5.2 SECONDARY EFFICACY ENDPOINTS

The secondary efficacy endpoints of the study are:

- Duration of response (DOR) defined as the time from the first documentation of response to the first documentation of progressive disease (PD) or death due to any cause
- Progression-free survival (PFS) defined as the time from the first dose of study treatment to the first documentation of PD or death due to any cause
- Overall survival (OS) defined as the time from the first dose of study treatment to the date of death
- Time to response (TTR), defined as the time from the first dose of study treatment to the first documentation of response (complete or partial)

5.3 EXPLORATORY EFFICACY ENDPOINT

The exploratory efficacy endpoint of this study is:

- Lymph node response rate (LNR rate), with LNR defined as $\geq 50\%$ reduction in the Sum of the Products of the Perpendicular Diameters (SPD) of nodal target lesions

5.4 SAFETY ENDPOINTS

The Safety endpoints include treatment-emergent adverse events (TEAEs), ECG measures, and changes in safety laboratory values.

5.5 PHARMACOKINETIC ENDPOINTS

Pharmacokinetics endpoint of the study is:

- PK parameters derived from plasma IPI-145 concentrations and, if applicable, its metabolite(s)

5.6 BIOMARKER ENDPOINTS

Biomarker endpoints of the study are:

- Serum, plasma and tissue biomarkers, and blood immunophenotype
- Tumor genomic features (e.g. DNA sequence variation, DNA copy number variation, and/or RNA expression)
- Germline DNA sequence variations

5.7 QUALITY OF LIFE ENDPOINTS

Health-related QoL of subjects as assessed by the following subject-reported questionnaire:

- EuroQol-5D (EQ-5D), a standardized instrument for use as a measure of health-related QoL

6 GENERAL STATISTICAL METHODS AND DATA HANDLING

6.1 GENERAL METHODS

Unless otherwise specified, categorical variables will be presented as frequencies and percentages, and continuous variables will be presented with the number of non-missing values, mean, standard deviation, median, minimum and maximum values. Graphs may also be presented where appropriate.

6.2 HANDLING OF MISSING DATA

For the purpose of calculating the duration from iNHL diagnosis or last anticancer therapy completion, partial/missing dates for iNHL diagnosis date and last anticancer therapy completion date will be imputed as follows:

- If both date and month are missing and the year is prior to the year of screening, the imputed date and month will be 01 July.
- If both date and month are missing and the year is the same as the year of screening, the imputed date will be the middle point between 01 Jan of the year and the screening date. If the middle point falls between two dates, the first of the two dates will be used.
- If date is missing and the month and year are prior to the month and year of screening, the imputed date will be 15th day of the month.
- If date is missing and the month and year are the same as the month and year of screening, the imputed date will be the middle point between the first date of the month and the screening date. If the middle point falls between two dates, the first of the two dates will be used.
- No imputation will be performed if the year is missing.

Details on handling partial/missing dates for AE and concomitant medications are provided in [Section 7](#).

6.3 MULTIPLE COMPARISONS/MULTIPLICITY

Not applicable for this study.

6.4 ADJUSTMENTS FOR COVARIATES

Adjustments for covariates will not be performed for this study.

6.5 SUBGROUPS

The primary endpoint and some secondary efficacy endpoints will be summarized by lymphoma subtypes. Details are available in [Section 7.2](#). In addition, the primary endpoint will be analysed for the following subgroups:

- Number of prior therapies (<3 or \geq 3)
- Number of prior therapies (1 or >1)
- Prior treatment with bendamustine (Yes or No)
- Refractory to bendamustine (Yes or No)
- Prior treatment with bendamustine-rituximab (Yes or No)
- Refractory to bendamustine-rituximab (Yes or No)
- FL subjects received only 1 prior therapy of bendamustine-rituximab and is refractory
- Refractory to last therapy status (Yes or No)
- Last therapy contains bendamustine and is refractory (Yes or No)
- Bulky status (Longest diameter of baseline lesion <5 cm or ≥ 5 cm)
- Gender (Male or Female)
- Age group (<65 or ≥ 65 years)
- Race (White or Non-White)
- Region (US or Non-US)

Refractory is defined as lack of a CR or PR on therapy or initiation of next therapy within 6 months (+ 30 days) of last dose.

6.6 METHODS OF POOLING DATA

No pooling will be performed for this study.

6.7 VISIT WINDOWS

Unless otherwise specified, the baseline value is defined as the most recent value prior to first study drug administration.

Treatment visits, cycles, and days are pre-defined for this study and are pre-specified on the CRF. In the presentation of study data using Study Day and Cycle Day, the following derivations will be used:

- Day 1 of Study = Date of first dose for a subject
- Study Day = Date – Date of first dose + 1, if Date is on or after Date of first dose; or Study Day = Date – Date of first dose, if Date is before Date of first dose
- Day 1 of Cycle = Date of cycle start, as reported on eCRF (per protocol, Day 1 of Cycle 1 should be Day 1 of Study)
- Cycle Day = Date – Date of cycle start in current cycle + 1

6.8 UNSCHEDULED VISITS

Unscheduled visits will only be included in listings and in post-baseline summaries of extreme values. Unless otherwise specified, unscheduled visits will not be included in the by-visit summaries.

6.9 COMPUTING AND CODING STANDARDS

Computing, coding and grading standards are provided in the following table.

Table 1: Computing, coding and grading standards

Table, listing, and figure production	SAS Version 9.2 or higher
Coding	
Adverse Events	MedDRA Version 16.1 or higher
Medical Histories	MedDRA Version 16.1 or higher
Prior and Concomitant Medications	WHODrug Version September 2013
Prior and post Systemic Therapy	WHODrug Version September 2013
Grading	
AEs	CTCAE Version 4.03
Laboratory Results	CTCAE Version 4.03

7 STATISTICAL ANALYSES

7.1 STUDY SUBJECTS

7.1.1 Disposition of Subjects

The number and percentage of subjects in each analysis set will be provided. This includes the FAS and the EAS. The percentage will be based on the number of subjects in the FAS.

Disposition of subjects will be summarized for the FAS. The number and percentage of subjects will be provided for those who are on treatment, those who discontinue treatment but are still in follow-up, and those who discontinue from the study. Further, subjects who discontinue treatment and those who discontinue from the study will each be summarized by reason for discontinuation. Disposition of subjects will be summarized for the overall population as well as by different disease subtypes.

Follow-up time (from 1st dose to last contact on or prior to data cut-off) will be descriptively summarized.

7.1.2 Demographic and Other Baseline Characteristics

Demographic characteristics include age, age category (<65 and ≥65), sex, race and ethnicity. Baseline characteristics include ECOG performance status, height, weight and BMI. These will be summarized for the FAS.

Disease diagnosis and staging will be summarized for both the FAS and EAS as follows: Translocations, FLIPI score at Screening, elevated LDH, Disease sub-type, NHL staging at diagnosis, NHL staging at entry, time from initial diagnosis to first dose date, baseline B-symptomatology, presence of bulky disease at baseline (any lymph node ≥5cm) and baseline cytopenia (≥Grade 3 neutropenia, ≥Grade 3 anemia, ≥Grade 3 thrombocytopenia). The imputation of partial/missing dates for time from initial diagnosis is provided in [Section 6.2](#). Presence of bulky disease is not directly collected and will be derived based on measurements of target lesions.

Demographics and baseline characteristics will be summarized for the overall population as well as by different disease subtypes.

7.1.3 Medical History

Medical history will be summarized by System Organ Class (SOC) and Preferred Term (PT), and sorted alphabetically in SOC and by decreasing frequency in PT. Medical history will be presented for the FAS.

7.1.4 Prior Therapies and Surgeries

Prior anticancer therapies will be summarized by ATC level 1, ATC level 2 and preferred drug name. Number of prior anticancer regimens (continuous and categorical) will be descriptively summarized.

The number and percentage of subjects treated with the following therapies will be provided: rituximab, rituximab induction monotherapy, bendamustine, alkylating agent, purine analogue, radioimmunotherapy, anthracycline, bendamustine-rituximab, combination of rituximab and alkylating agent, R-CHOP, R-CVP, and stem-cell transplant. The number and percentage of subjects who are refractory to the following therapies will be provided: rituximab, bendamustine, alkylating agent, purine analogue, radioimmunotherapy, anthracycline, bendamustine-rituximab, combination of rituximab and alkylating agent, R-CHOP, and R-CVP. Subjects who are refractory to 2 or more regimens and subjects who are refractory to last therapy will also be provided. The definition of refractory is provided in [Section 6.5](#).

Time since completion of last anticancer therapy to the first dose date will be summarized. Time since completion of the last rituximab therapy to the first dose date, and time since completion of last alkylating agent/purine analogue therapy to the first dose date will also be summarized. The imputation of partial/missing dates is provided in [Section 6.2](#).

Prior radiation and prior surgeries (Yes and No) will be presented.

Prior therapies, radiation and surgeries will be summarized for the FAS.

Prior therapies will be summarized for the overall population as well as by different disease subtypes.

7.1.5 Prior and Concomitant Medications

Prior medications are defined as medications that stopped prior to the first dose of study drug.

Concomitant medications include either of the following:

- Medications that started on or after the first dose date of study drug, up to 30 days post last dose.
- Medications that started prior to and continued after the first dose of study drug.

Both prior medications and concomitant medications will be summarized by ATC level 1, ATC level 2 and preferred drug name. The summary will be sorted by decreasing frequency in ATC level 1, ATC level 2 and preferred drug name. A subject taking the same drug multiple times will only be counted once.

No imputation will be performed for missing/partial onset or stop dates. Partial dates will be used if they are sufficient to determine whether medications are prior or concomitant. Otherwise, medications with partial onset and/or stop dates will be considered as concomitant. Medications with completely missing dates will be considered as concomitant.

7.1.6 Exposure to Study Drug

Extent of exposure to study drug will be characterized by:

- Total actual dose (mg) calculated as: Sum of all doses received throughout the study
- Duration (months) calculated as: (Last dose date – first dose date + 1) divided by 30.4375
- Dose Intensity (mg/day) calculated as: Total actual dose divided by duration in days
- Relative dose intensity (%) calculated as: Dose intensity divided by the intended dose intensity multiplied by 100. The intended dose intensity is 50 mg/day because the starting dose is 25 mg BID.
- Compliance rate (%) calculated as: total actual dose divided by the total prescribed dose multiplied by 100. The total prescribed dose is the sum of all doses prescribed throughout the study.

Total actual dose, duration (continuous and categorical), dose intensity, relative dose intensity and compliance rate will be descriptively summarized. The total number of cycles started (continuous and categorical) will also be provided. In addition, time on treatment phase, defined as time from first dose to date of decision to discontinue treatment will be provided.

Dose modification is characterized by dose reduction, dose interruption and dose increase. If the current non-zero prescribed dose level is lower (or higher) than the immediately preceding non-zero prescribed dose level, it is considered as a dose reduction (or increase), regardless of the dosing history prior to the immediately preceding dose. The number of dose reductions (1, 2, ≥ 3), dose interruptions (1, 2, ≥ 3) and dose increases (1, 2, ≥ 3) will be summarized. Dose reductions and interruptions due to adverse events as provided from the Active Treatment eCRF will be similarly summarized.

Exposure and dose modification will be summarized for the overall population as well as by different disease subtypes.

7.1.7 Protocol Deviations

Protocol deviations will be finalized prior to database release for the final analysis. Major protocol deviations will be summarized by type of deviation for the FAS. A listing will be provided for all major protocol deviations.

7.2 EFFICACY ANALYSES

Assessment of response and progression status will be evaluated locally (i.e. Investigator's assessment) and by an independent, third party panel of radiologists and oncologists (Independent Review Committee [IRC]) according to the revised IWG Response Criteria for Malignant Lymphoma¹. The IRC assessment will be used for the primary analyses of response and progression-based efficacy endpoints (e.g., ORR, PFS, TTR and DOR). Data based on local assessment will also be presented for these endpoints.

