CT scans of chest, abdomen and pelvis ^{a, b}	X	X	X ^c
Bone marrow aspirate and/or biopsy ^d	X	X	
Focused physical examination and assessment of B symptoms	X	X	X
Response Assessment ^e	X	X	X

- a. CT scans of the chest, abdomen and pelvis are required for all subjects to document measurable disease at Screening and will be performed within 7 days prior to initiating the next cycle of study treatment (i.e. Day -7 to Day 1) of Cycles 3, 5, 7, 10 and at every fourth cycle thereafter (Cycle 14, 18, 22, etc.) while on-treatment with IPI-145. Other scans may be performed (e.g. head/neck CT) if clinically indicated or to evaluate a site of known disease. Copies of all scans will be sent for independent review of response assessment.
- b. 18-FDG PET/CT scan or MRI may be substituted if clinically indicated, but the modality chosen to evaluate each individual subject should be the same throughout the duration of the study. The frequency provided is the minimum required for study participation.
- c. Scans will be performed at the EoT if the subject is discontinued for reasons other than radiologic disease progression and a previous assessment has not been performed within 30 days of the EoT visit.
- d. Bone marrow biopsy and/or bone marrow aspirate required only for subjects who otherwise meet the criteria for a CR unless the subject had an adequate bone marrow biopsy at Screening that was negative for lymphoma or unless the subject had previously undergone a bone marrow procedure confirming the CR. If bone marrow aspirate and/or bone marrow biopsy is performed, bone marrow biopsies and/or aspirate samples (along with corresponding pathology report, if available) should be sent for biomarker analysis if available.
- e. Response assessment is determined using information from objective measurements of available CT scan, focused physical exam, bone marrow biopsy as relevant, and assessment of B symptoms.

Table 4: Long-term Follow-up Assessments for IPI-145 Monotherapy

	Disease follow-up ^a		Survival Follow-up ^c
	≤ 12 months from 1st Dose of IPI-145 Every 12 weeks	>12 months from 1st Dose of IPI-145 Every 16 weeks	
Response assessment ^b	X		
Survival			X

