- a. For subjects who discontinue study treatment for reasons other than radiologic disease progression, response assessments (as shown in [Table 3](#)) will be performed during long-term follow-up. The same tumor assessments utilized during the treatment phase of the trial should be used during long-term follow-up. The first disease assessment follow-up should occur approximately 12-16 weeks after the last on-treatment/end-of-treatment tumor assessment. Response assessments following the long-term follow-up disease assessment schedule will occur for 2 years after the first dose of IPI-145 or until progression is documented or other anticancer therapy is initiated, whichever occurs first.
- b. Response assessment is determined using information from objective measurements of available CT scan, focused physical exam, bone marrow biopsy as relevant, and assessment of B symptoms.
- c. For all subjects who discontinue treatment from IPI-145, survival follow-up will occur every 6 months (\pm 4 weeks) from IPI-145 treatment discontinuation for up to 3 years after their first dose of IPI-145. This assessment can be conducted by telephone interview. Information on initiation of other anticancer therapy will also be collected and is to include start date and therapy name(s), of other subsequent therapies if applicable.

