4.4 TREATMENT DISCONTINUATION

A subject should be withdrawn from the study treatment if, in the opinion of the investigator, it is medically necessary, or if it is the wish of the subject. However, every effort should be made to keep the subject on study treatment. Subjects will be withdrawn from study treatment in case of any of the following reasons:

- An adverse event that requires permanent discontinuation of IPI-145
- Protocol-specified disease progression
- Subject death
- Noncompliance to protocol

- Investigator decision
- Subject becomes pregnant
- Termination of the study by sponsor
- Voluntary withdrawal from treatment by subject

In addition to the above reasons, other circumstances may necessitate discontinuation of a subject from the study treatment, as judged by the investigator or sponsor.

If a subject does not return for a scheduled visit, then every effort should be made to contact the subject. In any circumstance, every effort should be made to document subject outcome.

Adverse events (AEs) and SAEs leading to the discontinuation of a subject will be followed until resolution, resolution to baseline or until the event is considered chronic.

Subjects (including subjects that withdraw consent from study treatment but not overall study participation) must attend an End of Treatment Visit (EoT) (within 7 days following the decision to permanently discontinue study treatment) and a Safety Follow up Visit (30 +7 days from last dose of IPI-145) (Refer to Section 6.5.1 for further details). Subjects who have not withdrawn consent from overall study participation will enter long-term follow-up phase of the trial (see [Section 6.5.2](#)).

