6.3.13 Indolent NHL Response Assessments

All disease specific assessments are to be completed (see [Table 8](#)) and as outlined in [Table 3](#). The modality chosen to evaluate each individual subject should be the same throughout the duration of the study. Copies of all scans will be sent for independent review of response assessment.

CT scans of the chest, abdomen and pelvis are required for all subjects at Screening. These assessments may be performed within 7 days of initiating the next cycle of therapy (Day -7 to Day 1) of Cycles 3, 5, 7, 10, 14 and every fourth Cycle thereafter (Cycle 18, 22, etc.) until disease progression or start of other anticancer therapy. Copies of all scans will be sent for independent review of response assessment. Other scans may be performed (e. g, neck/head CT) if clinically indicated or if the area is a site of known disease. MRI may be substituted if clinically indicated, but the modality chosen to evaluate each individual subject should be the same throughout the duration of the study. The frequency outlined is the minimum required for study participation.

Scans will be performed at the EoT if the subject is discontinued for reasons other than radiological disease progression and a previous assessment has not been performed within 30 days of the EoT visit. If the subject has discontinued treatment for reasons other than disease progression, scans should be performed until disease progression or start of additional anticancer therapy (see [Table 3](#) for scan frequency).

Bone marrow biopsy and/or bone marrow aspirates are to be performed at Screening (where clinically indicated) and as required thereafter to confirm a complete response as per the revised IWG criteria.¹ If the screening samples are performed within 60 days of Cycle 1, Day 1 and frozen aspirate sample and unstained slides or blocks are available, these results can be used in place of the Screening assessment. If bone marrow aspirate and/or bone marrow biopsy is performed, the Screening and the post-Screening bone marrow biopsies and/or aspirate samples should be sent for biomarker analysis if available. See the IPI-145-06 Laboratory Manual for further instructions regarding the handling, shipping, and storage of the samples.

[Table 8](#) shows the major criteria employed for disease response assessment.

Table 8: Disease Response Criteria

Response	Definition	Nodal Masses	Spleen Liver	Bone Marrow

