6.5.2 Long-term Follow-up

For subjects discontinuing treatment due to reasons other than radiologic disease progression, disease assessments should occur for 2 years after the first dose of IPI-145 (following the on-treatment response assessment schedule, [Table 3](#)) or until documented disease progression or other anticancer therapy is initiated, whichever occurs first. Disease response scans will be performed at the EoT, every 12 weeks within the first year of the start of dosing and then every 16 weeks after a year since the start of dosing of study drug.

All subjects who permanently discontinue treatment with IPI-145 for reasons other than withdrawal of consent from overall study participation will enter survival follow-up. Survival follow-up will occur every 6 months (\pm 4 weeks) from permanently discontinuing IPI-145 treatment for up to 3 years after first dose of IPI-145 or until death. The assessments shown in [Table 4](#) can be conducted by telephone interview. Information on initiation of other anticancer therapy will also be collected.

Please see [Table 4](#) for more details on the long-term follow-up assessments.

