7.2.2 Analyses of Secondary Efficacy Endpoints

7.2.2.1 Progression Free Survival (PFS)

Censoring of PFS will be performed as detailed in Table 2 below. Note that progression may be documented based on scheduled or unscheduled disease status assessment, and that unscheduled disease status assessment may be included in calculating the gap between adequate disease status assessments.

PFS will be presented using the Kaplan-Meier method. A 2-sided 95% confidence interval for median PFS will be provided. PFS will be analysed for the FAS and the EAS with FAS being the primary analysis set. It will also be analysed for the follicular lymphoma population, as well as the other disease subtypes within the FAS.

Table 2: PFS and DOR censoring algorithm

Situation	Date of Event or Censoring	Outcome
No adequate baseline disease status assessment	Date of first dose	Censored
No adequate post-baseline disease status assessment unless death occurs prior to first post-baseline assessment	Date of first dose + 1	Censored
No documented progression or death before data cutoff	Date of last adequate disease status assessment	Censored

Situation	Date of Event or Censoring	Outcome
Documented progression with ≤ 1 missing scheduled disease status assessment before progression	Date of the earliest assessment that results in a finding of unequivocal progression	Event
Death before progression being documented with ≤ 1 missing scheduled disease status assessment before death	Date of death	Event
Documented progression or death following a long gap between adequate disease status assessments (e.g., 2 or more consecutive missed scheduled disease status assessments along with a gap of more than 6 months)	Date of last adequate disease status assessment before the gap	Censored
New anticancer treatment or procedure started before documented progression	Date of last adequate disease status assessment	Censored

Note: the first two rows are applicable to PFS only.

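### IRC-based DOR may be overstated: imaging ends at radiologic progression, by inference on the site's call, and site PD without IRC PD is then censored

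*SAP*

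**What the plan says.** **Assessor for the analysis.** SAP 7.2, in line with Protocol 9.4: "The IRC assessment will be used for the primary analyses of response and progression-based efficacy endpoints". It adds: "Data based on local assessment will also be presented for these endpoints".

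**When imaging stops.** Protocol 6.3.13 runs on-study scans "until disease progression or start of other anticancer therapy". Table 3, note c: "Scans will be performed at the EoT if the subject is discontinued for reasons other than radiologic disease progression", and then only if there is no assessment within the preceding 30 days. Protocol 6.5.2 covers the period after treatment: "For subjects discontinuing treatment due to reasons other than radiologic disease progression, disease assessments should occur for 2 years". Table 4, note a, restricts post-treatment response assessments to the same group.

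**What ends treatment.** Protocol 4.4 lists "Protocol-specified disease progression" among the reasons for withdrawal. Neither this section nor the imaging passages say whose reading counts. The IRC is described as receiving copies of the scans; no read-back or confirmation before withdrawal is described.

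**Censoring.** In SAP Table 2, the row "No documented progression or death before data cutoff" censors at the last adequate assessment. So does the row for new anticancer treatment started before documented progression. A death before documented progression is an event if at most one scheduled assessment was missed. SAP 7.2.2.2 applies the same table to DOR without its first two rows. No row deals with site PD that the IRC does not confirm. The only analysis labelled as a sensitivity analysis (SAP 7.2.1.2) concerns lymphocytosis and ORR in SLL.

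**The concern.** One assessor, apparently the site, decides when a subject stops being scanned. Another, the IRC, decides whether the primary PFS or DOR event has occurred. When the site sees radiologic progression and the IRC does not, no later scan exists on which the IRC could reach that finding. The subject leaves the risk set because the disease looked worse, whereas Kaplan-Meier assumes that censored subjects have the same future risk as those who remain. If many of these subjects were in fact progressing, the IRC curve sits too high, in the drug's favour.

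This matters most for DOR. The trial has a single arm with ORR as primary endpoint, and the durability of responses is the natural context for reading the rate.

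**Working it through.** **The plan's own figure.** No target or power is stated for PFS or DOR; both are descriptive Kaplan-Meier summaries. The one power figure is for ORR: above 90% with 120 subjects, 30% against 45%, one-sided 0.025. It reproduces. The smallest exact-binomial cut-off with alpha at most 0.025 is 47 responders, giving alpha 0.0200 and power 0.916 (0.910 if the trial stops at 7 or fewer of 30). Nothing below alters it.

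**Path of a subject with site PD but no IRC PD.**
1. Treatment ends for progression (Protocol 4.4).
2. Because the reason is radiologic progression, no end-of-treatment scan is required (Table 3, note c) and the subject does not enter post-treatment disease assessment (6.5.2; Table 4, note a).
3. The IRC data contain no PD. Table 2 therefore applies its no-progression row or its new-treatment row, and both censor at the last adequate assessment.
4. Exception: a death with at most one missed assessment is an event.

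**Size, simple model.** Assumptions, none from the documents: exponential DOR with true median m = 10 months, and a share d of all DOR events turned into censoring at the event time. The estimated hazard is then (1 − d) times the true one:
- median = m / (1 − d)
- 12-month rate = 0.5^(12(1 − d)/m)

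| d | median (months) | 12-month rate |
|---|---|---|
| 0 | 10.0 | 0.5^1.20 = 43.5% |
| 10% | 10/0.9 = 11.1 | 0.5^1.08 = 47.3% |
| 20% | 10/0.8 = 12.5 | 0.5^0.96 = 51.4% |
| 30% | 10/0.7 = 14.3 | 0.5^0.84 = 55.9% |

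**Allowing for deaths.** Deaths are DOR events but cannot be discordant. If a share q of events are deaths and d applies only to progressions, the median is m / (1 − d(1 − q)). With q = 20% (assumed), d = 10, 20 and 30% give 10/0.92 = 10.9, 10/0.84 = 11.9 and 10/0.76 = 13.2 months.

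**Size, second model.** Simulation of 200,000 responders with exponential DOR. Follow-up is uniform over 6 to 36 months from first dose (30-month accrual, final analysis about 6 months after the last first dose), less 1.8 months to response (the Phase 1 median, Protocol 1.5). In a share d of subjects, site PD comes before IRC PD by up to one four-cycle scan interval (4 × 28 / 30.4375 = 3.7 months). True median 10 months:

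| d | censored at site PD | site PD counted as event |
|---|---|---|
| 10% | 11.0 | 9.8 |
| 20% | 12.2 | 9.7 |
| 30% | 13.7 | 9.5 |

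Scanning on to IRC PD gives 10.0. For true medians of 6 and 15 months, the censored medians at d = 10, 20 and 30% are 6.5, 7.2 and 8.1, and 16.5, 18.5 and 21.0.

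**No-bias case.** If site-only PD is independent of later IRC PD, the censored median stays at 10.0 for every d. Counting site PD as an event then gives 9.3, 8.6 and 8.0 for d = 10, 20 and 30%.

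**The case against.** - **Local results are already planned.** For PFS this largely answers the point. Local PFS uses the same FAS subjects and the same start date and counts site PD as an event, so a further run would differ mainly by adding IRC-only or earlier IRC progressions. For DOR it does not. Local DOR uses local responders and local response dates, so a gap from IRC DOR mixes disagreement on response with disagreement on progression.
- **The documents do not say that the site decides.** Correct: the imaging and withdrawal passages name no assessor. The site's role is an inference from the absence of any IRC step before withdrawal.
- **Not everyone is affected.** Correct. An early death is still an event, and survival follow-up continues. Subjects stopped for clinical rather than radiologic progression remain eligible for the end-of-treatment scan and post-treatment assessments. The death exception is limited: a later death can fall under the long-gap or new-treatment row, and both censor.
- **The bias may be nil.** Correct if site-only PD carries no information about true progression. The documents cannot settle this, which is a reason to report the check.
- **Nothing is tested on DOR.** Correct. This limits the weight of the point but does not remove it.

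**Conclusion.** The mechanism follows from the text once the site is accepted as the party whose reading ends imaging. IRC DOR may be overstated; the same holds for PFS, but matters less there because local PFS is planned. What is missing is any analysis in IRC responders that shows how much the censoring matters.

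A reader might infer more: that IRC DOR is overstated as a fact, or that every subject with site PD alone is censored at that scan. The documents do not support either. They give no discordance rate and no link between site-only PD and true progression, and Table 2 keeps some deaths as events. Nor is there any consequence for ORR or its test.

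The illustration (10 months read as about 11.1, 12.5 or 14.3 for d = 10, 20 or 30%) rests on an assumed median, an assumed d and exponential durations, with every discordant call taken as a real event. It shrinks when some events are deaths and vanishes under independence. This is a cheap improvement to the SAP, not a flaw in the primary analysis.

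**What to change.** 1. Add to SAP 7.2.2.2 one sensitivity analysis of DOR in the IRC responders, starting at the IRC response date, with the event at the earliest of IRC PD, site PD or death. Show it beside the primary IRC estimate.
2. Report a cross-table of PD by IRC and by site, so that the number of discordant subjects is visible.
3. Optionally, add the matching PFS run to 7.2.2.1 as a supplement to local PFS.

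**Cost.** A few lines of SAP text, one extra DOR run (two if PFS is added) and one table. Both assessments are already collected, so no scan, read or treatment rule changes.

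**Downside.** The sensitivity estimate will be shorter. It falls slightly below the truth when the site calls PD early (9.5 to 9.8 against 10.0 months in the second model) and further below if site-only PD is unrelated to true progression (8.0 to 9.3). Label it a conservative bound, not a replacement for the primary estimate.
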